Day -60 or up to -30: Follow up visit within 2 months after visit 0 (optional): Safety and early effects of Stribild (safety labs) will be assessed.

Day 0: Baseline visit: prescription given for Genvoya; begin switch from TDF based regimen to TAF based regimen.

Day 60 (2 month follow up visit): Safety follow-up and early (2 month post switch) differential in vivo effects of TAF based regimen on mitochondrial health will be assessed.

Day 180 (6 month follow up visit): Late (6 month post switch) differential in vivo effects of TAF based regimen on mitochondrial health will be assessed.

Blood draws will be done at Day -90, Day 0, Day 60, Day 180 for laboratory testing. Approximately 100mL will be collected at each visit, with no more than 400 mL total over the course of the study.

Screening

Medical records will be accessed and reviewed for:

- HIV status (e.g. CD4 count, viral load)
- Age
- Underlying condition and comorbidities
- Medications
- Labs e.g. creatinine to determine kidney and liver function

Switch to Stribild: switch from any other ART→Stribild. No additional blood draw.

Participants will undergo a blood draw (100mL) and then be given a prescription for TAF based regimen for 6 months (switch from TDF→TAF).

Entry/Day 0

Follow-up phone call

2 weeks after the Entry visit, a brief phone call from the PI or study coordinator will be made to participants to ensure they are adjusting to the switch okay. The following questions will be asked:

- Are you tolerating the new medication okay?
- Have you experienced any new symptoms since you started the new drug? (expected side effects from switching antivirals should have already been addressed at the initial study visit).
- Have you been taking all your pills?
- Do you have any questions we could answer for you?

If new symptoms appear, the participant will be instructed to schedule a visit with their care provider for standard evaluations.

Day 60 post-switch
Blood draw (100mL)

Day 180 post-switch
Blood draw (100mL)

Laboratory Evaluations

Mitochondrial function assays: The Seahorse method measures function through the COC (increased COC indicates reduced bioenergetic capacity and mitochondrial dysfunction).

Specimen Preparation, Handling and Shipping

Whole blood will be collected using standard phlebotomy and placed in standard heparin green top tubes. All tubes per participant will be placed in a biohazard bag and shipped at room temperature to [name] Lab for further processing.

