Ship to: [name] Lab/Infectious Diseases
[name]
[name]

Total Blood Volume

100 mL of blood will be collected during Day -90, Day 0, Day 60, and Day 180. No more than 400mL of blood will be collected for this study.

CARE Clinic will draw and collect blood to be sent to [name] lab via courier. [name] lab will handle all blood processing, including peripheral blood mononuclear cells (PBMCs),

Entry visit

- Fasting Lipid Profile

The following labs are to be done only if they have not been done within the last 3 months:

- CBC
- Complete metabolic panel
- HIV RNA PCR
- CMV antibody

Safety labs for Visit 2:

- HIV viral load
- T-cell subset
- CBC
- CMP
- Fasting Lipid Profile
-

Safety labs for Visit 3:

- CBC
- CMP
- Fasting lipid profile

100 ml of blood will be drawn per visit/phlebotomy. Out of this volume standard tubes for the standard clinical

labs (fasting lipid profile, complete metabolic panel, HIV RNA PCR, CMV antibody, T- cell subset) will be sent to the clinical laboratory as per standard clinic procedure. The rest of the whole blood will be placed in EDTA or green top tubes and will be shipped to [name] lab via courier. It is expected that 1 million cells will be obtained per ml of whole blood and cells will be isolated and cryopreserved at [name] lab.

ASSESSMENT OF SAFETY

Adverse Event Reporting and monitoring.

An AE is any unfavorable and unintended sign (including an abnormal laboratory finding), symptom, or diagnosis that occurs in a study participant during the conduct of the study REGARDLESS of the attribution (i.e., relationship of event to medical treatment/study product/device or procedure/intervention). This includes any occurrence that is new in onset or aggravated in severity or frequency from the baseline condition. The Division of AIDS Table for Grading the Severity of Adult and Pediatric Adverse Events (DAIDS AE Grading Table), corrected Version 2.1, July 2017, must be used for grading the adverse events in this protocol and is available on the DAIDS RSC Web site at <http://rsc.tech-res.com/clinical-research-sites/safety-reporting/daids-grading-tables>.

The AEs/SAEs should immediately be reported to the Principal Investigator. All events should be reported to the local IRB if they are reportable per the local IRB's reporting criteria.

This study will be internally monitored biannually.

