Cellular oxygen consumption (COC): From all the measures of mitochondrial function **cellular oxygen consumption (COC)** will be considered the “gold standard” given it is a measure of the most important mitochondrial function (oxidative phosphorylation) that relates to clinical outcome. It is accepted that two independent measures of mitochondrial function can more reliably predict mitochondrial dysfunction compared to each one of the measures separately. Thus, given the uncertainty of what measure of mitochondrial function can best predict NRTI-induced mitochondrial toxicity, comparison of relative fold induction of mitochondrial dysfunction in PBMC compared to baseline measurement will be done.

Primary endpoint is continuous variables (measured in pmoles O₂/min) and it will be compared between the 2 groups on different antiretrovirals (TAF based vs TDF based) cross sectionally using unpaired t-test. Changes in primary outcome within the same person will be determined by paired t-test (baseline and after switch). Statistical p value <0.05 will be considered statistically significant.

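### Is the primary endpoint, cellular oxygen consumption, too loosely defined for its result to be read?

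*Combined protocol and SAP*

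**What the plan says.** The Study Schema names COC as the primary outcome and makes the other mitochondrial measures secondary. Laboratory Evaluations gives the platform and the only rule of interpretation: "The Seahorse method measures function through the COC (increased COC indicates reduced bioenergetic capacity and mitochondrial dysfunction".

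Primary Endpoint (Statistical Considerations) justifies the choice because "it is a measure of the most important mitochondrial function (oxidative phosphorylation) that relates to clinical outcome". On the analysis it says "Primary endpoint is continuous variables (measured in pmoles" of O₂ per minute. It compares that quantity between TAF and TDF by unpaired t-test and within persons by paired t-test, with significance at p<0.05. The same section, "given the uncertainty of what measure of mitochondrial function can best predict NRTI-induced mitochondrial toxicity", adds that "comparison of relative fold induction of mitochondrial dysfunction in PBMC compared to baseline measurement will be done".

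On specimens, Specimen Preparation, Handling and Shipping has blood "placed in standard heparin green top tubes". Total Blood Volume says "The rest of the whole blood will be placed in EDTA or green top tubes", and also "It is expected that 1 million cells will be obtained per ml of whole blood and cells will be isolated and cryopreserved".

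Neither the protocol nor its statistical section states which respiration parameter COC is, how the assay is run, how many cells are loaded, or whether the rate is divided by cell number.

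**The concern.** Three things look wrong at first.

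- **COC could be formed in several ways.** It might be a basal or a maximal rate, per well or per cell, from fresh or thawed cells. The study is open-label and the investigator sees all data, so the form could be chosen once results are known.
- **Two forms of result sit in one section.** There is a raw rate and a fold relative to baseline. The fold has no formula, is not tied to COC and carries no test.
- **The sign is unexplained.** The trial asks which form of tenofovir is worse for mitochondria, so the direction of COC is the answer. The plan reads a rise as harm, yet it selects COC as a measure of oxidative phosphorylation, and a reader might expect more of that to mean better function. No p-value would reveal a wrong sign.

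If these points held, the main conclusion could be selected after the fact or reported the wrong way round.

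**Working it through.** The documents give no SD, effect size or power for COC, so there is no stated figure to reproduce. Every CV, SD, correlation and effect size below is an assumption. The 30 participants and the 0.05 level come from the plan; two-sided testing and 30 complete pairs are assumed.

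**1. Which scale is tested.** Primary Endpoint runs in one sequence: continuous variable, unit, unpaired t-test, paired t-test, p<0.05. All of these attach to the rate in pmoles O₂/min. The fold sentence has no test, threshold or formula, and its subject is mitochondrial dysfunction, not COC. As written, the raw rate is analysed and the fold is descriptive.

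**2. If the fold were tested all the same.** Take log-normal COC with the same distribution before and after the switch, between-person CV c and log-scale within-person correlation r. The log variance is ln(1+c²). The log ratio has mean 0 and variance 2(1−r)ln(1+c²), so

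E[post/baseline] = (1+c²)^(1−r).

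| c | r = 0.8 | r = 0.5 | r = 0.3 |
|---|---|---|---|
| 0.2 | 1.008 | 1.020 | 1.028 |
| 0.3 | 1.017 | 1.044 | 1.062 |
| 0.5 | 1.046 | 1.118 | 1.169 |

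Simulation over the same nine cells, 30 pairs, no true effect:

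- A one-sample t-test of fold against 1 rejects in about 6% to 18% of trials, mostly upward (4.4% to 17.7%, against a nominal 2.5%).
- The raw paired test that the plan specifies rejects in 4.8% to 5.1%.
- Mean raw change is below zero while mean fold exceeds 1 in 13% to 42% of trials, but these are mostly two non-significant means.
- Raw and fold were never both significant in opposite directions. A significantly raised fold with a negative raw mean occurred in at most about 0.1% of trials (at c = 0.5, r = 0.3).

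The inflation therefore belongs to a test that is absent from the plan, and conflicting significant results almost never arise.

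**3. Normalisation.** Raw rate = cells × rate per cell. With 10% more cells and a 5% lower rate per cell, 1.10 × 0.95 = 1.045: raw up 4.5%, per-cell down 5%. For this to be a trial result, the 10% must be an average shift over 30 people after the switch. If cell number varies independently between visits with CV 10%, the mean shift has standard error

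0.10 × √2 / √30 = 0.026,

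so 10% is nearly 4 standard errors (0.10/0.026 = 3.8). No passage suggests a systematic visit difference in cell number.

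Random variation costs power instead. The SD of the paired log difference is √2 × √(s² + ln(1+CV²)), where s is the within-person log SD. For an assumed 20% change and s = 0.2:

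| Cell-number CV | SD of log difference | Power, 30 pairs |
|---|---|---|
| 0 | 0.283 | 93% |
| 10% | 0.316 | 86% |
| 20% | 0.398 | 68% |
| 30% | 0.502 | 49% |

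**4. Direction.** Laboratory Evaluations states a sign in advance. Primary Endpoint states none. The two texts sit uneasily together but do not contradict each other, and nothing in the documents shows which sign is right. The t-test and the estimated change in pmoles O₂/min are the same whichever label is attached, so a reader can see whether COC rose or fell.

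**5. Specimens.** The wider tube statement includes the heparin tube of the narrower one, and no passage assigns EDTA blood to COC. Cryopreservation is the only storage described, so thawed cells is the natural reading.

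**The case for a change.** The strongest case for a change is that a named primary endpoint should have one definition before anyone sees data, however exploratory the study. No laboratory manual is cited for COC, and a manual would not settle which form the analysis treats as primary. If any of k definitions could be reported at p<0.05, the false-positive rate under independence is 1 − 0.95^k: 9.8% for k = 2, 18.6% for k = 4 and 26.5% for k = 6. At an assumed correlation of 0.9 between definitions it is about 7.0%, 9.9% and 11.0%. A few sentences would remove the doubt at almost no cost.

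The omissions are real and that much stands: parameter, run conditions and normaliser are unnamed, the fold is undefined, and the direction has no rationale. The k-fold figures, however, describe picking the best of several results, which the plan neither proposes nor implies; it names one primary outcome and calls the other measures secondary. The investigator's access to all data is given as a reason for having no monitoring board, not as an analysis provision. A laboratory cannot run the assay without fixing cells per well and fresh or thawed material, and a sensible analyst would keep these constant across a person's visits. On direction, asking for a reason is a request for clarification; it does not identify a rule shown to be wrong.

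**Conclusion.** No change to the plan follows. This is missing detail of the kind that the laboratory and analyst fill in, not an analysis rule that would give a wrong answer. The scale, both tests and the significance level are stated for the primary endpoint, and the raw paired test holds its level (4.8% to 5.1% in simulation). The 6% to 18% false-positive range applies only if someone averages post/baseline ratios and tests them against 1, which the plan does not specify. A sign reversal through cell number needs a systematic shift between visits that no passage suggests; random variation reduces power, by an amount that cannot be known without COC variability data.

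This conclusion assumes that one COC form is used consistently across visits and that the reported change keeps its sign and unit. It also gives weight to the plan's own statement, under Assessment of Safety, that the study is small and exploratory and needs confirmation in larger trials. Whether the stated direction is correct cannot be settled from these documents.

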An open-label switch study will be conducted in virologically-suppressed, HIV-1 positive participants. The switch regiment will be: 1) Stribild®; elvitegravir 150 mg/cobicistat 150 mg/emtricitabine 200 mg/tenofovir disoproxil fumarate 300 mg; E/C/F/TDF) to Genvoya; elvitegravir 150 mg/cobicistat 150 mg/emtricitabine 200 mg/tenofovir alafenamide 10 mg; E/C/F/TAF OR 2) Complera (Emtricitabine/Rilpivirine/Tenofovir Disoproxil Fumarate Tablets) to ODEFSEY (25 mg rilpivirine + 200mg emtricitabine + 25mg tenofovir alafenamide fumarate) OR 3) TRUVADA (emtricitabine/tenofovir disoproxil fumarate) + any other combination of antivirals to Descovy (200 mg emtricitabine + 10 mg tenofovir alafenamide fumarate).

Major eligibility criteria for study participants will be age > 18 years old, any CD4 T cell count, viral load <50 copies/ml or undetectable on E/C/F/TDF for the previous 3 months prior to the onset of study, adequate renal function determined by the Cockcroft-Gault formula for creatinine clearance and no evidence of acute hepatitis in the prior 30 days. Major exclusion criteria will be pregnancy and diseases or use of other drugs known to affect mitochondrial function. Subjects will have three clinical visits: one at baseline prior to the TDF to TAF switch, and follow up visits at 2 and 6 months after the switch. We will also include the option to switch ANY HIV-infected person who meets the inclusion criteria and not on an antiretroviral regimen other than Stribild [(Elvitegravir (ELV)/cobicistat (CO)/emtricitabine (FTC)/tenofovir (TDF)] to switch to Stribild for 3 months. This will allow for future switch (after these 3 months) from Stribild to GENVOYA. This approach can expedite recruitment since we can switch HIV infected persons to Stribild and then do another switch from Stribild to GENVOYA as per study protocol. In addition given the known clinical benefits (less toxicity) of Stribild and Complera compared to older antiretrovirals (such as protease inhibitors) [Patient Prefer Adherence. 2015; 9: 1213–1218.; J Acquir Immune Defic Syndr. 2014 Mar 1; 65(3):e118-20; Lancet. 2012 Jun 30;379(9835):2439-48; J Acquir Immune Defic Syndr. 2014 Mar 1; 65(3):e121-4; AIDS. 2012;26:2315–2326; J Infect Dis. 2015;212(3):345–354] and the known clinical benefits of TAF compared to TDF (less bone and kidney toxicity) these ART switches are beneficial for the participant and they also allow us to study differential effects of TAF

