vs TDF on mitochondria. The participants who will undergo any ART switch will have a clinic visit or a phone call 1-2 weeks after the ART switch to check for side effects/tolerability of the new regimen and all subjects will have a clinic visit with blood tests to check viral load and safety labs (complete metabolic panel and complete blood count) within 2 months after any switch. Then after informed consent has been obtained ART will be switched as per protocol.

During visits at baseline, month 2, 6, blood will be obtained for isolation of PBMC (measurement of mitochondrial function). This study design will account for confounders that may affect mitochondrial function among different subjects (given the intrinsic heterogeneity of mitochondria). All study participants will be recruited in outpatient clinics within UCLA. All HIV-1 infected participants will be recruited within the UCLA Center for AIDS Education and Research (UCLA CARE) Center which provides HIV care to over 1000 patients with HIV in Los Angeles and is regarded as one of the premier HIV care providers in the country. We anticipate recruiting 60 (30 HIV-1 infected and 30 uninfected) persons in total for all outlined experiments.

STUDY POPULATION

HIV-1-infected participants in the Los Angeles area will be recruited voluntarily through a UCLA IRB-approved protocol at UCLA Center for AIDS Research and Education (CARE).

Enrollment will be open to men and women from all socioeconomic strata and all race and ethnic groups. We anticipate enrolling 30 HIV-1 infected individuals in total.

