4.2 Exclusion Criteria

- History of taking medications that are known to have a major effect on mitochondrial function such as cyclosporine, mitochondrial antioxidants.
- History of mitochondrial disease
- Pregnancy
- Hepatitis; no evidence of acute hepatitis in the prior 30 days
- History of severe renal impairment (eGFR < 30 ml/min/1.73 m²)
- History of severe or recent cardiac event
- Current alcoholism or IV drug abuse
- Use of systemic immunomodulatory medications (e.g. steroids) within 4 weeks of enrollment
- Anemia precluding safe donation of blood (For men, anemia is typically defined as hemoglobin level of less than 13.5 gram/100 ml and in women as hemoglobin of less than 12.0 gram/100 ml).
- Use of any investigational products within 4 weeks of enrollment
- Any other clinical condition or prior therapy that, in the opinion of the investigator, would make the patient unsuitable for the study or unable to comply with the study requirements. Such conditions

may include, but are not limited to, current or recent history of severe, progressive, or uncontrolled renal, hepatic, hematological, gastrointestinal, endocrine, pulmonary, neurological, or cerebral disease.

- Subjects who are on medications that are strong inducers of CYP3A (as these may decrease the efficacy of Stribild or Genvoya). Examples include phenobarbital, phenytoin, carbamazepine, and rifampin.
- Subjects who are on medications that are cleared by CYP3A and that may be toxic with elevated drug levels (examples include Cisapride, ergotamine, Pimozide, Lurasidone, Lovastatin, and Simvastatin).

INTERVENTIONS

Regimen (dose, schedule, route, administration)

Scenario 1: TAF based regimen is **Genvoya**

Study Switch (Stribild → Genvoya)

Intervention: Genvoya (elvitegravir 150 mg/cobicistat 150 mg/emtricitabine 200 mg/tenofovir alafenamide 10 mg; E/C/F/TAF) (1 tablet orally once daily for 6 months)

Scenario 2: TAF based regimen is ODEFSEY

Study Switch (Complera (Emtricitabine/Rilpivirine/Tenofovir Disoproxil Fumarate Tablets) □ ODEFSEY® (emtricitabine, rilpivirine, and tenofovir alafenamide). Intervention: ODEFSEY (25 mg rilpivirine + 200mg emtricitabine + 25mg tenofovir alafenamide fumarate)

Scenario 3: TAF based regimen is Descovy

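### The Entry metabolic panel may be up to 3 months old, so it can predate the whole 30-day acute-hepatitis window and is a loose baseline for post-switch liver and kidney results (minor)

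*Combined protocol and SAP*

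**What the plan says.** - **Eligibility.** Section 4.2 lists "Hepatitis; no evidence of acute hepatitis in the prior 30 days", and the Study Design section repeats the 30-day wording. Neither says whether the 30 days run back from enrolment, from the optional switch to Stribild (Day -90) or from Day 0.
- **Entry labs.** Under Total Blood Volume, the Entry visit requires a fasting lipid profile from everyone. For CBC, metabolic panel, HIV RNA and CMV antibody it says "The following labs are to be done only if they have not been done within the last 3 months". No hepatitis serology or separate liver test is listed.
- **Screening.** This is a review of medical records. It covers "Underlying condition and comorbidities" and "Labs e.g. creatinine to determine kidney and liver function", with no limit on the age of the results.
- **Run-in participants.** The Schedule of Events puts a follow-up visit with safety labs between Day -60 and Day -30 and marks it optional. The Study Design section has all subjects undergo "safety labs (complete metabolic panel and complete blood count) within 2 months after any switch".
- **Day 0.** 100 mL is drawn and the TAF prescription is then given. Tubes for the clinical laboratory come out of that volume.
- **After the switch.** The metabolic panel is repeated at Visits 2 and 3. Assessment of Safety counts an abnormal laboratory finding as an adverse event if it is new or worse relative to the baseline condition.

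**The concern.** Two look-back periods bear on the same liver information and differ by a factor of three. A site that follows every instruction can enrol a participant whose latest liver result predates the entire exclusion window. Unless the records show otherwise, that participant meets the criterion because nothing has been looked for.

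The more general consequence concerns the safety baseline. If the Entry panel is skipped, the last known pre-switch liver and kidney values may be up to 3 months old. A rise that developed before Day 0 would first be seen at Visit 2, on the new regimen, and could be recorded as a post-switch event. This applies to any intercurrent liver or kidney abnormality, not only to hepatitis. It has some weight here because the study has no randomised concurrent control, and because the discontinuation criteria take participants off study for adverse effects of grade 3 or higher.

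**Working it through.** The plan gives no figure on this point, so there is none to reproduce. The check compares time windows.

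**Inputs.** Exclusion window: 30 days (section 4.2; Study Design). Permitted age of a reused panel: 3 months, taken as 90 days (Entry visit list). Run-in safety labs: Day -60 to -30 (Schedule of Events). Visits 2 and 3: Days 60 and 180. Assumptions: the metabolic panel includes liver enzymes (its components are not listed), and the 30 days are counted back from Day 0.

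**1. Ratio of windows.** 90 / 30 = 3. A panel aged 31 to 90 days may be reused but lies wholly before the exclusion window.

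**2. Share of reused panels older than 30 days.** This depends on the distribution of ages over 0 to 90 days, which the documents do not give:

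| Assumed distribution of age | Formula | Share older than 30 days |
|---|---|---|
| Uniform | (90 - 30) / 90 | 66.7% |
| Recent-weighted triangular | ((90 - 30) / 90)² | 44.4% |
| Truncated exponential, scale 30 days | (e⁻¹ - e⁻³) / (1 - e⁻³) | 33.5% |
| Old-weighted triangular | 1 - (30 / 90)² | 88.9% |

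Taking 3 months as 91 or 92 days moves the uniform figure only to 67.0% or 67.4%. These shapes are illustrations, not bounds. The share exceeds one half only if the median age of reused panels exceeds 30 days.

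**3. Run-in participants.** No distribution is needed here. Labs at Day -60 to -30 are 30 to 60 days old at Day 0. All are at or beyond the edge of the window, and all are under 90 days, so each could replace the Entry panel.

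**4. Safety comparison.** With a Day 0 panel, the comparison spans 60 days at Visit 2 and 180 days at Visit 3. With a 90-day-old panel it spans up to 60 + 90 = 150 days and 180 + 90 = 270 days. Up to 90 / 150 = 60% of the Visit 2 interval and 90 / 270 = 33% of the Visit 3 interval would then lie before the switch.

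**The case against.** The strongest reply is that no rule is broken. The criterion asks for "no evidence of acute hepatitis in the prior 30 days", which history and record review can satisfy, and the protocol never says that the Entry panel is the test of it. Screening covers comorbidities and liver-function labs, and section 4.2 lets the investigator exclude anyone with recent serious hepatic disease. That stands: the criterion does not rest on one blood test, and the two rules can both be obeyed.

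Several stronger readings are tempting, and the documents do not support them:

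- **That most reused panels are useless for the criterion.** The share older than 30 days is unknown. An older abnormal panel can still flag hepatitis that persists into the window; only onset after the test is missed.
- **That the exclusion fails for a stated part of the 30 participants.** Any such count needs the clinic's testing interval, which is not given. It would also count old panels, not cases of hepatitis.
- **That screening relies on creatinine to assess the liver.** Creatinine is given only as an example, so this is loose drafting.
- **That the primary comparison is biased.** Blood for COC is drawn at Day 0 in every case, so that baseline is not stale. Nothing in the documents gives the direction or size of any effect of hepatitis on COC in PBMCs.

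Two further replies also stand in part. Adverse events are recorded regardless of attribution, so a misdated rise is not automatically ascribed to TAF, and the baseline condition is not defined as the reused panel. And a panel drawn on Day 0 need not be back before the prescription is given.

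**Conclusion.** The point holds in a limited form. Reuse for up to 3 months allows the Entry panel to predate the whole 30-day window and miss hepatitis that began after it. For run-in participants who reuse their safety labs, this follows from the protocol's own schedule if the window is counted from Day 0. The same reuse leaves up to 90 pre-switch days inside the interval over which post-switch liver and kidney changes are judged.

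The size is uncertain. The proportion of reused panels older than 30 days is 67% under uniform ages and about 33% to 89% under the other shapes tried. Acute hepatitis is probably rare, so few participants, perhaps none, would be wrongly enrolled. The conclusion assumes that the metabolic panel carries liver enzymes and, for eligibility, that the window runs back from Day 0; the safety-baseline part does not depend on that anchor. Severity is minor: the change is worth making mainly because it is cheap and gives a laboratory baseline at the switch.

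**What to change.** 1. In the Entry visit list under Total Blood Volume, take the metabolic panel out of the 3-month reuse rule and run it for every participant from the blood already drawn at Day 0.
2. Name that panel as the baseline for liver and kidney laboratory adverse events at Visits 2 and 3.
3. Reconcile the 30-day window in section 4.2 and Study Design with the permitted age of the liver result, and state the anchor date, including for run-in participants.
4. State whether the result is reviewed before the switch. A Day 0 draw is enough for the safety baseline, but it informs eligibility only if the result is seen before the prescription is given.
5. Reword the Screening line on kidney and liver function so that it names liver tests.

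**Cost.** A short amendment, and one extra routine chemistry tube for participants who have a recent panel. A lipid profile already goes to the clinical laboratory at Entry and clinical tubes come out of the 100 mL, so no added visit or blood volume is needed for the baseline. If the result must be seen first, there is a short wait or an earlier draw.
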